#### 7.2.2 Assessment of adverse events

Investigators will assess the occurrence of adverse events and serious adverse events at all subject evaluation time points during the study. All adverse events and serious adverse events whether volunteered by the subject, discovered by study personnel during questioning, detected through physical examination, clinically significant laboratory test, or other means, will be recorded. Each recorded adverse event or serious adverse event will be described by its duration (i.e., start and end dates), severity, regulatory seriousness criteria (if applicable), suspected relationship to the investigational product, and any actions taken.

#### 7.2.3 Adverse Event Reporting Period

All AEs whether serious or non-serious, will be captured from the time signed and dated Informed Consent Form (ICF) is obtained until 30 days following the last dose of study drugs or until the initiation of alternative anticancer therapy. Progressive disease should NOT be reported as an

event term, but instead symptoms/clinical signs of disease progression may be reported. All Grade 3 – 5 adverse events, regardless of seriousness, severity, or presumed relationship to study drug, must be recorded using medical terminology in the source document. All records will need to capture the details of the duration and the severity of each episode, the action taken with respect to the study drug, investigator's evaluation of its relationship to the study drug, and the event outcome. Whenever possible, diagnoses should be given when signs and symptoms are due to a common etiology (e.g., cough, runny nose, sneezing, sore throat, and head congestion should be reported as "upper respiratory infection").

All deaths should be reported with the primary cause of death as the AE term, as death is typically the outcome of the event, not the event itself.

#### 7.2.4 Other events requiring reporting

##### Overdose

An overdose is defined as a subject receiving a dose of study combination in excess of that specified in this protocol. If the overdose results in an AE, the AE must also be recorded as an AE. Overdose does not automatically make an AE serious, but if the consequences of the overdose are serious, for example death or hospitalization, the event is serious and must be recorded and reported as an SAE. The investigator will use clinical judgment to treat any overdose.

##### Pregnancy

Before study enrollment, subjects must agree to take appropriate measures to avoid pregnancy. However, should a pregnancy occur in a female study subject, consent to provide follow-up information regarding the outcome of the pregnancy and the health of the infant until 30 days old will be requested.

A female subject must immediately inform the Investigator if she becomes pregnant from the time of consent to 30 days after the last dose of study combination. A male subject must immediately inform the Investigator if his partner becomes pregnant from the time of consent to 3 months after the last dose of study drug. Any female subjects receiving study drug(s) who become pregnant

must immediately discontinue study drug. The Investigator should counsel the subject, discussing any risks of continuing the pregnancy and any possible effects on the fetus.

Although pregnancy itself is not regarded as an adverse event, the outcome will need to be documented. Any pregnancy occurring in a subject or subject's partner from the time of consent to 30 days after the last dose of study combination must be reported. Any occurrence of pregnancy must be reported per SAE reporting timelines. All pregnancies will be followed for outcome, which is defined as elective termination of the pregnancy, miscarriage, or delivery of the fetus. Pregnancies with an outcome of live birth, the newborn infant will be followed until 30 days old by completing will need to be reported per SAE reporting timelines. Any congenital anomaly/birth defect noted in the infant must be reported as a serious adverse event.

#### Paternal Exposure

Pregnancy of the subject's partners is not considered to be an adverse event. However, the outcome of all pregnancies (spontaneous miscarriage, elective termination, ectopic pregnancy, normal birth or congenital abnormality) should if possible be followed up and documented.

To capture information about a pregnancy from the partner of a male subject, the male subject's partner consent must be obtained to collect information related to the pregnancy and outcome; the male subject should not be asked to provide this information. A consent form specific to this situation must be used. The outcome of any conception occurring from the date of the first dose until 6 months after dosing ends should be followed up and documented.

#### Other Malignancies

All new malignant tumors including solid tumors, skin malignancies and hematologic malignancies will be reported for the duration of study treatment and during any protocol-specified follow-up periods including post-progression follow-up for overall survival.

The investigator (or physician designee) is responsible for verifying and providing source documentation for all adverse events and assigning the attribution for all adverse events for subjects enrolled.

### **8. Recording and Collection of Data**

#### Case report forms

Electronic case report forms will be used for this study, stored under the Data Management Initiative (DMI) database. All data collection and storage will be performed under the DMI platform. Use of concomitant medications is routinely captured in the patient's electronic medical record and the information is readily available if it needs to be obtained for analysis of study results. As such, concomitant medications will not be captured in DMI.

### **9. Statistical Consideration**

#### 9.1 Definitions

All efficacy analyses will be performed in all eligible patients enrolled. Safety analyses will be performed on all patients who received any dose of any treatment.

1. Objective Response Rate (ORR) is the percent of patients whose best response is complete response or partial response as determined by RECIST 1.1 criteria.
2. irORR is the percent of patients whose best response is immune-related complete response (ir-CR) or immune-related partial response (ir-PR) as determined by irRECIST criteria.
3. Progression-free survival (PFS) is defined as the duration of time from start of treatment to time of progression or death, whichever occurs first. PFS rate at 6 months is the percentage of patients without disease progression at these time-point.
4. Overall survival (OS) is defined as the duration of time from start of treatment to death. OS rate at 6 months is the percentage of alive patients at these time-point
5. The duration of overall response is measured from the time measurement criteria are met for CR or PR (whichever is first recorded) until the first date that recurrent or progressive disease is objectively documented (taking as reference for progressive disease the smallest measurements recorded since the treatment started).

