## 3. Study Design

### 3.1 Study Design

This is a Phase II, single center open label, study to determine the safety and efficacy of axitinib and avelumab combination in patients with recurrent or metastatic adenoid cystic carcinoma (ACC) with evidence of disease progression within 6 months prior to study enrollment.

Up to 30 patients will be treated with a combination of axitinib 5 mg orally twice a day and avelumab 10mg/kg intravenously every two weeks. A treatment cycle will be 28 days. Treatment will continue until disease progression, death, unacceptable toxicity or consent withdrawal.

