## 9.2 Analysis plan

This is a single-arm, phase II trial to assess the efficacy of the combination of axitinib and avelumab in patients with recurrent or metastatic adenoid cystic carcinoma (ACC) with disease progression within 6 months prior to study enrollment. The primary endpoint is the overall response rate by RECIST 1.1. The trial will be conducted by Simon's 2-stage design and the response rate will be estimated after the second stage (Simon, 1989).

It is assumed that the new regimen will have a target overall response rate at 6 months of 20%. A response rate of 5% or lower is considered a failure and the new regimen will be rejected under this circumstance. When the probability of accepting a "bad" regimen (i.e. ORR $\leq$ 5%) is 0.05 and the probability of rejecting a "good" regimen (i.e. ORR  $\geq$ 20%) is 0.20, Simon's Optimal design requires to enter 10 patients in the first stage. If no patient responds to the treatment, the trial will be stopped and the regimen will be declared as ineffective. If there are one or more responses, 19 more patients will be entered in the study to reach a total of 29 evaluable patients. To ensure that we have 29 evaluable patients we will enroll a total of 30 patients. By the end of the study, the new regimen will be rejected if response rate at 6 months is less than or equal to 3/29 and will be accepted otherwise. The operating characteristics of the trial are given as follows. When the true response rate is 0.05 the probability of stopping the trial early is 60%. On the other hand, if the true response rate is 0.20, the probability to stop the trial early is 10.7%. The expected sample sizes are 17.6 and 27.0 when the true response rates are 0.05 and 0.20, respectively.

To ensure patient safety, the toxicity monitoring will be carried out from the 7th patient using the stopping boundaries calculated based on the beta-binomial distribution. The target toxicity rate by the end of cycle 1 (4 weeks of treatment) is 30%. Toxicity is defined as: as adverse events in the first 4 weeks that are judged to be attributable to one agent or both in combination. Relevant hematological events are grade 4 anemia, grade 4 neutropenia lasting longer than 7 days, febrile

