### Target Disease

Complete Response (CR): Complete disappearance of all target lesions with the exception of nodal disease. All target nodes must decrease to normal size (short axis < 10 mm). All target lesions must be assessed.

Partial Response (PR): Greater than or equal to 30% decrease under baseline of the sum of diameters of all target measurable lesions. All target lesions must be assessed.

Stable Disease (SD): Does not qualify for CR, PR or Progression. All target lesions must be assessed. Stable can follow PR only in the rare case that the sum increases by less than 20% from the nadir (smallest sum of diameters consider baseline and all assessments prior to the time point under evaluation), but enough that a previously documented 30% decrease no longer holds. Objective Progression (PD): 20% increase in the sum of diameters of target measurable lesions above the smallest sum observed (over baseline if no decrease in the sum is observed during therapy) with a minimum absolute increase of 5 mm.

Not evaluable (NE): Progression has not been documented, and one or more target lesions have not been assessed; or assessment methods used were inconsistent with those used at baseline; or one or more target lesions cannot be measured accurately (e.g., poorly visible unless due to being too small to measure); or one or more target lesions were excised or irradiated and have not reappeared or increased.

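### Section 9.1 analyses efficacy in all eligible enrolled patients, but section 9.2 decides on 29 evaluable patients, a term not defined for a patient, with no rule for any other final number

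*Combined protocol and SAP*

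**What the plan says.** Section 9.1 defines one efficacy population: "All efficacy analyses will be performed in all eligible patients enrolled". Section 3.1 sets the maximum: "Up to 30 patients will be treated with a combination of axitinib".

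Section 9.2 describes the primary decision in other terms. Simon's optimal design "requires to enter 10 patients in the first stage". If at least one patient responds, "19 more patients will be entered in the study to reach a total of 29 evaluable patients". The margin is one patient: "To ensure that we have 29 evaluable patients we will enroll a total of 30 patients". At the end the regimen is "rejected if response rate at 6 months is less than or equal to 3/29 and will be accepted otherwise". The last part of 9.2 then places the final response review after 30 patients, not 29.

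Section 9.2 uses *evaluable* for patients in both the efficacy and the toxicity rules, but no section defines it for a patient. The nearest definition, in Appendix 1 under Target Disease, is a status at a single tumour assessment: "Not evaluable (NE): Progression has not been documented, and one or more target lesions have not been assessed".

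**The concern.** The two sections can give the primary endpoint different denominators. A 30th patient enrolled to guarantee 29 evaluable ones implies that some enrolled patients may not count. Section 9.1 allows that only for ineligible patients. If 9.2 also means eligible patients who cannot be assessed, it removes people whom 9.1 keeps.

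Those people are unlikely to be a random subset. On-treatment imaging is every 8 weeks (section 6), and Appendix 1 requires CR and PR to be confirmed by measurements at least 4 weeks apart. A patient who stops early may therefore have no usable scan. Such a patient has no recorded response, so leaving the patient out can only raise the observed response rate.

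The plan also does not say which 29 patients decide if all 30 qualify, or what cut-off applies if fewer than 29 do. In an open-label single-arm trial, settling these questions after responses are known would let the primary result depend on the choice.

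**Working it through.** **Inputs (section 9.2).** Unacceptable rate p0 = 0.05; target rate p1 = 0.20; error limits 0.05 and 0.20; stop if there are 0 responders among the first 10; reject if 3 or fewer respond among 29.

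**Formula.** With a first stage of 10, a final n, and acceptance at 4 or more responders,

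P(accept) = P[Bin(n, p) ≥ 4] − (1 − p)^10 × P[Bin(n − 10, p) ≥ 4].

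The subtracted term removes the paths that stop at stage 1. At p0 this is alpha, and at p1 it is power.

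**The plan's own figures.**
- Early stopping: 0.95^10 = 0.599 and 0.80^10 = 0.107 (stated 60% and 10.7%).
- Expected sample size: 10 + 19 × (1 − 0.599) = 17.6 and 10 + 19 × (1 − 0.107) = 27.0, as stated.
- Alpha at n = 29: 0.05475 − 0.59874 × 0.01324 = 0.0468.
- Power at n = 29: 0.85962 − 0.10737 × 0.54491 = 0.8011.

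A search over designs for the smallest expected sample size under p0 also returns 0/10 and 3/29. The stated design is reproduced.

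**Other final numbers, cut-off kept as a count (accept with at least 4).**

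| Final n | Alpha | Power |
|---|---|---|
| 30 | 0.0513 | 0.814 |
| 29 | 0.0468 | 0.801 |
| 28 | 0.0426 | 0.786 |
| 27 | 0.0385 | 0.769 |

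Only n = 29 meets both stated limits. At n = 30, raising the requirement to 5 responders gives alpha 0.0141 but power 0.705, so changing the cut-off there does not restore both.

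**The cut-off taken literally as a rate.** 3/29 = 10.3%. At n = 30, 3 responders (10.0%) reject and 4 (13.3%) accept, so the two readings agree. At n = 28, 3/28 = 10.7%, and at n = 27, 3/27 = 11.1%. Both exceed 10.3%, so 3 responders would accept. The same formula with 3 in place of 4 gives:
- n = 28: 0.16266 − 0.59874 × 0.05813 = 0.128.
- n = 27: 0.15049 − 0.59874 × 0.05025 = 0.120.

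**How often n falls below 29.** The documents give no rate of non-evaluable patients. If 2%, 5% or 10% of 30 do not count (assumptions), the chance that 28 or fewer remain is 0.12, 0.45 or 0.82.

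**Effect on the estimate.** Suppose there are 4 responders and 3 of 30 eligible patients have no usable scan (an assumption). ORR is 4/30 = 13.3% (exact 95% CI 3.8 to 30.7) with them counted, and 4/27 = 14.8% (4.2 to 33.7) with them dropped. If they are not replaced, the count rule accepts either way.

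**The case against.** The best defence is that 9.1 already settles the denominator. It names one population without exception and defines ORR by best response, so a patient with no usable scan has no response and counts as a non-responder. The final review after 30 patients fits that, and *evaluable* could simply mean eligible, with the 30th patient covering someone later found ineligible. This reading is coherent and may be what was meant. It remains an inference: no text equates the two words or states how unassessed patients are counted. It also leaves open which 29 decide when all 30 are eligible, and what applies below 29.

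Three stronger readings are tempting, but the documents do not support them.

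- A reader might infer that the trial's false-positive rate is really 12% to 13%. That needs 3/29 to be applied as a rate at n = 28 or 27. Section 9.2 names Simon's design, for which 3 of 29 is a count boundary, and the count is the natural reading.
- A reader might infer that every early failure would leave the denominator. Under Appendix 1, NE applies only where progression has not been documented. A patient with documented progression is PD and stays in, and Appendix 1 asks for every effort to document PD after treatment stops.
- A reader might infer that the plan intends to drop unassessed patients. It does not say so. It only fails to exclude it.

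It is also fair to say that the effect on the decision is small: under the count rule, dropping unassessed patients without replacement changes the estimate but not the decision.

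**Conclusion.** The inconsistency is real and should be fixed, but it is not an error in the design arithmetic, which is exact at n = 29. What remains open is the denominator of the primary ORR and its confidence interval, and the rule when the final number is not 29.

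With the count rule the error rates move modestly: alpha to 0.051 with all 30, and power to 0.786 or 0.769 with 28 or 27. The upward bias in ORR arises only if eligible patients with no usable post-baseline scan and no documented progression are dropped. Its size depends on how many there are, which the documents do not give; in the example above it is 1.5 percentage points. The rate wording is a secondary drafting weakness. All error rates here assume independent responses and the first stage held at 10.

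**What to change.** - In 9.2, replace *evaluable* with the 9.1 population at both stages, so that stage 1 is the first 10 eligible patients.
- State that any eligible patient without a usable post-baseline assessment counts as a non-responder in the ORR and its confidence interval.
- Make the decision on the first 29 eligible patients in order of enrolment, and write the cut-off as a count: accept only with at least 4 responders (alpha 0.047, power 0.801).
- Report ORR in all eligible enrolled patients, and say in 9.1 that the decision rule alone uses the first 29.
- If fewer than 29 are eligible, keep the requirement of at least 4 and report the attained alpha and power (n = 28: 0.0426 and 0.786; n = 27: 0.0385 and 0.769).

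This costs a few sentences and no more patients. ORR may be slightly lower because unassessed patients count as non-responders. The power of 0.801 then refers to a 20% response rate with those patients included.

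If all 30 are eligible, the decision can also reject at 3/29 while 4/30 is reported. The probability of that is p × {P[Bin(29, p) = 3] − (1 − p)^10 × P[Bin(19, p) = 3]}. At p = 0.05 it is 0.05 × (0.1204 − 0.0319) = 0.4%. At true rates of 10%, 15% and 20% it is 1.7%, 2.0% and 1.3%. The report should say in advance that the first-29 result decides.

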### 2.2 Secondary objectives

- Assess ORR to axitinib and avelumab combination according to irRECIST criteria patients with recurrent or metastatic adenoid cystic carcinoma (ACC)
- Evaluate median progression free survival (PFS), PFS rate at 6 months after start of treatment
- Evaluate median overall survival (OS), OS rate at 6 months after start of treatment
- Evaluate duration of response (DoR)
- Evaluate safety and toxicity

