# Proprietary of MD Anderson Cancer Center

EKG	X			
Echocardiogram	X	X 		
Urine analysis for proteinuria	X	X 		
Pregnancy Test (serum or urine) for all women of child bearing potential 	X	X 		
Radiology & Tumor Measurements 	X	X Every 8 weeks, ± 7 days		X
Biopsy	X If archived tissue not available			
Blood-based biomarkers	X 	X 		
Study Drug Compliance		X At each clinic visit		
Subsequent Anticancer Therapy				X
Survival Status				X

1 Written informed consent will be given by each patient prior to undergoing protocol specific evaluation and prior to receiving treatment

2 Chemistry profile includes: BUN, creatinine, sodium, potassium, carbon dioxide, magnesium, total bilirubin, alkaline phosphatase, aspartate aminotransferase, alanine aminotransferase, total protein, and serum phosphorus

3 Serum or urine pregnancy test will be obtained at baseline within 7 days prior to treatment and monthly during treatment in all women of child bearing age and again if clinically indicated

4 CT scan, PET CT scan of the chest/abdomen/pelvis and/or MRI of base of skull/orbit/face as clinically indicated. CT scan or MRI of the brain if clinically indicated

5 Long term follow-up will occur every 6 months by medical/clinical data review or phone contact

6 For patients who discontinue treatment due to reasons other than disease progression, tumor assessment will continue as per during the treatment schedule (i.e. radiology & tumor measurements every 8 weeks +/- 7 days).

7 Extended safety follow up: given the potential risk of immune-related toxicity, safety follow up will be performed up to 90 days after the last dose of avelumab administration. The extended follow up beyond 30 days after last avelumab administration may be performed either via a site visit or via a telephone call with subsequent site visit requested in case any concerns noted during the telephone call

8 Blood will be collected on at baseline (pre-treatment), day 7 (optional), day 15, prior to C3D1, and at progression (optional). Three categories of specimen will be collected: EDTA Vacutainer (checkpoint markers/CAFs): 10 mL = 1 x 10 mL; Streck CF-DNA BCT (ctDNA): 10 mL = 1 x 10 mL; and Sodium Heparin (immunoprofiling): 60 mL = 6 x 10 mL. All blood will be collected and processed by the Thoracic Research Team ([name] laboratory) according the institutional and laboratory standard operating procedures (SOPs).

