# Proprietary of MD Anderson Cancer Center

The above stopping boundaries and operating characteristics are calculated using MultcLean (v.2.1.0) design software downloaded from <http://biostatistics.mdanderson.org/SoftwareDownload>.

Summary statistics including mean, standard deviation, median, and range for the continuous variables, and frequency tables for categorical variables, will be provided. The response rate will be estimated along with its 95% confidence interval. The distribution of time-to-event endpoints including overall survival, progression free survival and duration of response will be estimated using the method of Kaplan and Meier.

The investigator is responsible for completing an efficacy/safety summary report. The efficacy report will be reviewed by the principal investigator and/or study co-chair. For Toxicity monitoring: This will be performed after the first 7 evaluable patients per cohort, complete 1 cycle of study treatment, and every 3 evaluable patients thereafter.

For Response assessment: After the first 10 patients and after 30 patients complete 6 months post-treatment.

A copy of the cohort summary will be placed in the Investigator's Regulatory Binder.

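### Section 9.1 words the 6-month PFS and OS rates as simple percentages, does not tie them to the planned Kaplan-Meier analysis, and leaves death out of the 6-month PFS rate

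*Combined protocol and SAP*

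**What the plan says.** Section 2.2 lists the 6-month rates as secondary objectives beside the medians: "Evaluate median progression free survival (PFS), PFS rate at 6 months after start of treatment". A parallel bullet covers OS.

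Section 9.1 sets the analysis set: "All efficacy analyses will be performed in all eligible patients enrolled". Items 1 and 2 define ORR and irORR as a percent of patients. Item 3 then gives two sentences on PFS. The endpoint comes first: "Progression-free survival (PFS) is defined as the duration of time from start of treatment to time of progression or death, whichever occurs first". The rate follows: "PFS rate at 6 months is the percentage of patients without disease progression at these time-point". Item 4 does the same for survival: "OS rate at 6 months is the percentage of alive patients at these time-point".

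Section 9.2, in the paragraph on summary statistics after Table 9, says of the time-to-event distributions that OS, "progression free survival and duration of response will be estimated using the method of Kaplan and Meier". It promises a 95% confidence interval for the response rate only. It mentions neither the medians nor the 6-month rates.

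No section gives a censoring rule for PFS or OS, or says how a patient of unknown status at 6 months is counted.

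**The concern.** Two named secondary endpoints have a definition in one section and a likely estimator in another, with nothing joining them. The definition follows the ORR wording and sits under an analysis set of eligible enrolled patients, so a programmer could reasonably compute a plain proportion. A plain proportion must put a patient who leaves before 6 months without an event into the numerator, count that patient as a failure, or drop the patient. None of these is generally the right treatment of a censored observation, and the plan does not choose among them. The choice could therefore be made after the data are seen, and the reported rate might not match the plan's own curve at 6 months.

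Item 3 has a second gap that does not depend on drop-out. PFS ends at progression or death, but the 6-month rate mentions progression only. Taken literally, a patient who dies before 6 months without progression counts as a 6-month PFS success.

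Exit without an event is foreseen: section 3.1 allows for consent withdrawal, and section 5.9 for refusal and loss to follow-up.

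**Working it through.** **The plan's own figures.** The documents state no target, sample size or power for the 6-month rates, so there is nothing to reproduce for them. The Simon design for ORR does reproduce. The early-stop probability is 0.95^10 = 0.599 at a 5% response rate and 0.80^10 = 0.107 at 20%. The expected sizes are 10 + 19 × (1 − 0.599) = 17.6 and 10 + 19 × (1 − 0.107) = 27.0. Exact type I error is 0.047 and power 0.801. None of this uses the 6-month PFS or OS rates.

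**Inputs for the drop-out check (all assumed, since the documents give none).** True 6-month rate S; probability d of leaving by 6 months if no event occurred; exponential event and drop-out times, independent of each other.

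**Formulas.** Let a = −ln S and c = −ln(1 − d).

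- Known event-free at 6 months: K = S(1 − d)
- Observed event by 6 months: E = [a/(a + c)] × (1 − K)
- Lost first: L = [c/(a + c)] × (1 − K)
- Proportion with leavers as successes: 1 − E; as failures: K; excluded: K/(1 − L)
- Kaplan-Meier target: S

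**Worked case, S = 0.60, d = 0.10.** a = 0.511, c = 0.105, K = 0.540. E = (0.511/0.616) × 0.460 = 0.381 and L = 0.079. Leavers as successes: 1 − 0.381 = 61.9%. As failures: 54.0%. Excluded: 0.540/0.921 = 58.6%. Kaplan-Meier: 60.0%.

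| S | d | Leavers as successes | As failures | Excluded | Kaplan-Meier |
|---|---|---|---|---|---|
| 60% | 5% | 60.9% | 57.0% | 59.3% | 60.0% |
| 60% | 10% | 61.9% | 54.0% | 58.6% | 60.0% |
| 60% | 20% | 63.8% | 48.0% | 57.0% | 60.0% |
| 90% | 5% | 90.2% | 85.5% | 89.8% | 90.0% |
| 90% | 10% | 90.5% | 81.0% | 89.5% | 90.0% |

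The 90% rows stand in for a possible OS rate. Over S from 50% to 90% and d from 5% to 20%, the error runs from +0.2 to +4.6 points (successes), −2.5 to −18.0 (failures) and −0.2 to −3.2 (excluded).

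**Small example.** Assume 29 patients with events at 1.8 months (4), 3.7 months (4) and 5.5 months (3).

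- No leavers: all methods give 18/29 = 62.1%.
- One leaver at 2.5 months: Kaplan-Meier = (25/29) × (20/24) × (17/20) = 61.1%. The proportions are 18/29 = 62.1% (success), 17/29 = 58.6% (failure) and 17/28 = 60.7% (excluded).
- One leaver at 1 month, before any event: Kaplan-Meier = (24/28) × (20/24) × (17/20) = 60.7%, equal to exclusion (17/28).

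**Death.** Each death without progression before 6 months that is counted as a success adds one patient to the numerator: 1/29 = 3.4 points, or 1/10 = 10 points if the trial stops after stage 1. The documents give no expected number of such deaths.

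**Scale.** The binomial standard error at 60% with 30 patients is √(0.60 × 0.40/30) = 0.089, about 9 points.

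**The case against.** The strongest reply is that nothing here contradicts anything. Section 9.1 says what the quantity is and section 9.2 says how time-to-event endpoints are estimated. The percentage alive at a time-point is also an ordinary description of a Kaplan-Meier estimate. Section 2.2 pairs each rate with its median, and 9.2 names neither; if the median is read from the curve, so presumably is the rate. This stands in part. A reader might infer that the plan prescribes two conflicting estimators, but the text never says crude or observed proportion. What remains is a definition not linked to its estimator.

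A reader might also infer that the PFS rate must be biased upward and the OS rate downward. That adds words the plan does not contain: it does not say without *recorded* progression, or *known* to be alive. The direction depends on a counting rule that the plan does not give. Nor is the rate biased whenever any patient leaves: the example above shows that excluding a patient who leaves before the first event gives the Kaplan-Meier value exactly.

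The plan also limits early loss. Table 6, footnote 6 continues 8-weekly imaging after treatment stops for reasons other than progression. Footnote 5 covers later contact: "Long term follow-up will occur every 6 months by medical/clinical data review or phone contact". Final response assessment waits until 30 patients complete 6 months, although that timing is stated for response only. These provisions reduce the number of unknowns but do not reach patients who refuse or cannot be traced, and they do not say how to count them.

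The reply does not answer the omission of death in item 3, which is an inconsistency within the item itself.

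**Conclusion.** The point holds as a gap in definition with a small expected effect. The two rates are worded as percentages of patients, are not tied to the Kaplan-Meier analysis, and have no rule for early loss; the 6-month PFS rate also omits death.

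At an assumed true rate of 60% and 5-10% drop-out, the error is about +1 to +2 points if leavers count as progression-free and −3 to −6 points if they count as failures, against a standard error near 9 points. The 20% scenario is shown for range only. The nearest figure in the documents is 3 of 55 consent withdrawals in the renal combination study (section 1.4), or 5.5%. Those are reasons for stopping treatment over a median follow-up of 52.1 weeks, not losses by 6 months, so the lower scenarios are the more plausible. With complete 6-month follow-up the drop-out error is zero; the death omission would remain if any patient died without progression.

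The endpoints are secondary and descriptive, with no test or threshold. The primary ORR analysis and the Simon decision rules are unaffected. The change is still worth making because it settles the estimator before the data are seen.

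**What to change.** Replace the rate sentences in section 9.1, items 3 and 4, with wording such as:

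*The 6-month PFS and OS rates are the Kaplan-Meier estimates at 6 months from start of treatment, reported with 95% confidence intervals. The event is progression or death for PFS and death for OS. Patients without an event are censored at the last adequate tumor assessment (PFS) or the last date known alive (OS).*

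This closes both gaps. The cost is a few sentences in 9.1. It needs no extra patients, visits or data items, and the curves are already planned in 9.2.
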